- Subcutaneous adipose tissue (3-5 g) will be removed from the abdominal region by aspiration with a 16-gauge needle under local anesthesia. A representative portion of the tissue will be handled as noted above. A portion of the tissue will be snap frozen in liquid nitrogen for subsequent RNA extraction and microarray analyses (see below). An aliquot of fresh adipose tissue will be transported immediately to [name] laboratory for the *in vitro* adipocyte studies (see below).

c. *Rosiglitazone intervention:*

Following the initial metabolic testing and sample acquisition, the subjects will initiate rosiglitazone therapy at 4 mg/day. At 4 weeks following the initiation, subjects will be evaluated by [name], Pharm.D., in order to ensure that there are no adverse effects from rosiglitazone therapy. Although liver dysfunction is much less common with rosiglitazone than troglitazone, we will measure serum ALT concentrations monthly. Medication compliance will be monitored using Trackcap (Medication Event Management Systems; Aprex Corp.), and by pill counting at each monthly visit. Frequent telephone contact will be maintained. If rosiglitazone is tolerated well after 4 weeks of treatment, the dose will be increased to the maximum dose of 8 mg (4 mg twice per day). We have chosen the maximum dose for rosiglitazone since to maximize the differences between responders and nonresponders. At each monthly visit, rosiglitazone drug levels will be measured to control for differences in drug when analyzing responsiveness.

d. *Metabolic testing after rosiglitazone therapy:*

After 12 weeks of rosiglitazone therapy, subjects will repeat metabolic testing identical to that described above taking place before the rosiglitazone intervention. Three months of therapy was chosen as the end point for the metabolic studies since by this time, rosiglitazone will have had its maximal effects on insulin sensitivity, the primary response outcome. Results of metabolic testing and clinical outcomes will be compared to the identical tests performed 12 weeks earlier (prior to the initiation to rosiglitazone) in the same subject.

e. *Analysis plan:*

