Screening will consist of medical history, vital signs, physical exam, and blood tests (a comprehensive chemistry profile, CBC, TSH, pregnancy test, 75 gram oral glucose tolerance test). Based upon this testing, subjects will be excluded if they have (1) stage III or greater congestive heart failure, symptomatic peripheral vascular disease, or stroke; (2) severe hypertension (BP>170/100); (3) anemia; (4) thyroid, pituitary, kidney or liver disease; (5) diabetes; (6) weight loss or gain of >5 kg in the previous six months; (6) hormone replacement therapy; (7) excessive use of caffeine (greater than three caffeinated drinks per day), or alcohol (greater than 3 ounces of liquor, or 3 x 4 ounce glasses of wine, or 3 x 12 ounce cans of beer per day); (8) use of medications that may affect glucose or lipid metabolism including beta blockers, thiazide diuretics, hypolipidemic agents, thyroid hormone, or

weight loss medications or formulas; (9) smoking >1/2 pack per day of cigarettes; and (10) pregnancy by urine testing.

Individuals with diabetes will be excluded because their metabolic control may vary, their likely use of multiple of multiple medications, and possible complications. From a statistical point of view, each source of variation can be regarded as an additional error term, requiring a much larger sample size for the same amount of power.

b. Sources of materials

Blood samples, urine samples, tissue samples, and results of physiological tests.

c. Potential risks

We expect no physical, psychological, social, or legal risks from a subject's participation in this protocol. Subjects who are screened, but not selected for participation for any reason will be referred to their primary health care provider for follow-up. Some of the procedures (DXA and CT scans) involve exposure to low doses of radioactivity; so pregnant women will be excluded from the study.

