When used in combination with other oral antidiabetic agents or insulin, rosiglitazone demonstrates additive effects. In combination with metformin, rosiglitazone 8 mg daily reduced HgbA1c by 0.8% when compared to baseline and 52% of patients were considered responders (28, 70). Similar reductions in HgbA1c and response rates have been observed in trials combining rosiglitazone and a sulfonylurea (28) or insulin therapy (65).

(4) Adverse effects/precautions

Rosiglitazone therapy is associated with weight gain (70). In clinical trials, the mean increase in weight was 3.5 kg in patients treated with 8 mg per day when given as monotherapy. Metformin attenuates the amount of weight gain associated with rosiglitazone therapy. Some of this weight gain may be attributable to an increased plasma volume and mild to moderate lower extremity edema (incidence 5%). Mild anemia, reported in 1.9% of patients on rosiglitazone monotherapy, may also be attributable to increased plasma volume. The incidence of all other reported side effects were similar to placebo.

In clinical trials and during post-marketing surveillance, rosiglitazone has not been associated with hepatotoxicity. Troglitazone, another member of the thiazolidinedione class of drugs, has been implicated in numerous cases of severe hepatotoxicity, thus requiring meticulous liver enzyme (ALT) monitoring. In clinical trials, significant elevations in serum ALT (greater than 3 times the upper limit of normal) was observed in only 0.2% of patients treated with rosiglitazone compared with a 0.2% incidence with placebo and a 0.5% incidence with metformin, insulin, and sulfonylureas. Evidence to date suggests that rosiglitazone is a safer medication than troglitazone with regard to liver toxicity. However, given their structural similarities, periodic serum ALT monitoring is recommended.

(5) Use in non-diabetic individuals

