We will heed the WARNINGS included in the rosiglitazone Product Information. We will monitor every four weeks for adverse events, including those mentioned in the Product Information, i.e., lower extremity edema and anemia. Patients will be questioned and examined at each visit regarding leg swelling. Rosiglitazone therapy will be decreased or discontinued in case of adverse events that are likely to be related to the drug. A complete blood count will be obtained at baseline and after 12 weeks to monitor for a decline in red blood cell concentrations as well as any other hematological derangements. Individuals with preexisting fluid retention or heart failure are ineligible for the study.

Although evidence indicates that rosiglitazone does not share the hepatotoxicity of troglitazone, we will monitor alanine transaminase every four weeks.

Subjects will be cautioned about the possibility of rosiglitazone to produce ovulation in some premenopausal women who might think themselves infertile. Adequate contraception in premenopausal women will be recommended.

Rosiglitazone will not be used in patients in whom it is CONTRAINDICATED (known hypersensitivity to the product or any of its components).

Genetic testing: Since the clinical relevance of the genetic testing is not yet proven, subjects will not be given any genetic information. If, in the future as a result of these studies or studies of others, gene variants that have clinical relevance are detected, all subjects who were genotyped will be contacted and first asked if they wish to know the result of their genotype analysis. If they do wish to be informed of their genotype, they will be informed by the investigators with the assistance of a genetics counselor, and with advice from an ethicist. However, subjects are given the option to decline all future genetic information when signing the consent form.

2. Adequacy of Protection Against Risks

a. Recruitment and informed consent

Written informed consent will be obtained from all subjects. The IRB approved consent form will be given to each subject, and informed written consent will be obtained by one of the investigators or a study coordinator following a personal interview with each subject. Subjects will be encouraged to read the consent form closely and the rationale, methods, potential risks and benefits of the interventions will be explained.

b. Protection against risks

Please see potential risks section above.

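### No blood count is scheduled between baseline and week 12, so symptom-free anemia cannot inform the week-4 dose increase or any dose reduction during treatment

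*Combined protocol and SAP*

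**What the plan says.** Section E.1.c, Rosiglitazone item (5), sets out the safety monitoring for non-diabetic volunteers: "We will monitor every four weeks for adverse events, including those mentioned in the Product Information, i.e., lower extremity edema and anemia". For edema it names a method at each visit, namely questioning and examination of the legs. For red cells it says: "A complete blood count will be obtained at baseline and after 12 weeks to monitor for a decline in red blood cell concentrations". The rule for action is: "Rosiglitazone therapy will be decreased or discontinued in case of adverse events that are likely to be related to the drug".

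Section D.2.c starts treatment at 4 mg/day, with a safety evaluation at four weeks. It continues: "If rosiglitazone is tolerated well after 4 weeks of treatment, the dose will be increased", to 8 mg daily. The monthly blood tests are ALT ("we will measure serum ALT concentrations monthly") and the rosiglitazone level. Metabolic testing follows after 12 weeks (Section D.2.d).

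At entry, Section E.1.a lists "blood tests (a comprehensive chemistry profile, CBC, TSH, pregnancy test, 75 gram oral glucose tolerance test" and continues "Based upon this testing, subjects will be excluded if they have" any of several conditions, one of which is anemia. No hemoglobin cut-off is given.

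On frequency, item (4) of the Rosiglitazone text in Section E.1.c says: "Mild anemia, reported in 1.9% of patients on rosiglitazone monotherapy, may also be attributable to increased plasma volume".

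**The concern.** The plan names two adverse events for four-weekly attention. One has a method that works at that interval. The other is normally established by a blood count, and no count is scheduled at week 4 or week 8.

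Two decisions are affected: whether to double the dose at week 4, and whether to reduce or stop the drug afterwards. A participant whose hemoglobin falls without symptoms would go to the maximum dose and stay on it for eight weeks. The fall would be seen only at week 12. Section E.5 then requires follow-up of the event, but no study dose remains to be adjusted.

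At entry the plan does not rely on symptoms, because the testing behind the anemia exclusion includes a blood count. The participants are non-diabetic volunteers on what item (5) itself describes as an unlabeled use, so a cheap safety check has some claim to be made.

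**Working it through.** The point is about a schedule, and the plan states no figure to reproduce. The schedule comes first, then the scale.

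**Schedule, from Sections D.2.b to D.2.d, E.1.a and E.1.c**

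| Time | Dose decision | Scheduled safety blood tests | Blood count? |
|---|---|---|---|
| Screening/baseline | Start 4 mg/day | Screening chemistry and blood count | Yes |
| Week 4 | Increase to 8 mg/day if tolerated | ALT, drug level | No |
| Week 8 | Continue, reduce or stop | ALT, drug level | No |
| Week 12 | None; course complete | End-of-course testing | Yes |

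The metabolic blood panel in Section D.2.b lists no blood count, hemoglobin or hematocrit. So neither of the two interim monthly visits has a hematology test, although blood is drawn at both. Time at 8 mg without a scheduled interim count is 12 − 4 = 8 of the 12 weeks.

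**Scale**

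Inputs: 75 participants (Section D.2.a) and a 1.9% rate of mild anemia (Section E.1.c, item (4)). The 1% and 3% rates are assumptions that bracket it.

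- Expected cases over the whole course = 75 × rate: 75 × 0.019 = 1.425; 75 × 0.01 = 0.75; 75 × 0.03 = 2.25.
- Chance of at least one case = 1 − (1 − rate)^75: 76% at 1.9%, 53% at 1%, 90% at 3%.
- Cases present by week 4: the documents do not give the timing of onset. At 1.9% the expected number lies between 0 and 1.425. An even spread over 12 weeks, assumed only for illustration, gives 1.425 × 4/12 = 0.475.

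**Does the pilot settle it?** Item (5) reports no drug-related adverse events in the ongoing study, and Section C.4 gives 11 completers. At 1.9%, the chance of no case in 11 is 0.981^11 = 0.81. An uneventful pilot is what one would expect even if the 1.9% rate applied.

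**The case against.** The strongest reply is that Section E.1.c describes two tiers: a clinical review every four weeks, and a laboratory check at the start and end. Where the plan wants a four-weekly laboratory test it says so, as it does for ALT. This stands. A reader might infer that the two sentences contradict each other; they do not, because monitoring for adverse events every four weeks does not promise a blood count every four weeks.

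A reader might also infer that anemia, or all mild anemia, must go unnoticed until week 12. The documents do not support that. Mild anemia with symptoms could surface at the week-4 evaluation, by telephone or at a four-weekly review, and nothing bars an unscheduled count. The gap is confined to symptom-free anemia.

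Three further objections carry weight.

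- **No automatic trigger.** The increase depends on tolerability, and the reduction rule depends on adverse events likely to be drug-related. Neither says that a symptom-free laboratory fall qualifies. Section E.5 leaves clinical significance of results to the principal investigator, so a week-4 count might change no dose. But the investigator cannot judge a result that has not been obtained.
- **Borrowed rate.** The 1.9% refers to rosiglitazone monotherapy, with no stated duration and no placebo rate. Item (5) says the drug is approved for diabetic patients. Here exposure is 12 weeks in non-diabetic volunteers screened for anemia, so the rate may be lower. The documents also call the anemia mild and possibly due to plasma volume.
- **Selective dosing.** Keeping affected participants at 4 mg ties dose to a drug effect. Section B.2 attributes fluid retention to PPARγ and reports a genetic association with it, while item (4) links the anemia to plasma volume. Adjusting for drug level does not remove selection of that kind. The existing tolerability and reduce-or-stop rules already create the same difficulty, so added counts would extend it slightly.

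**Conclusion.** The point holds in a narrow form. If the plan is followed as written, symptom-free anemia cannot inform the week-4 increase or any reduction during the following eight weeks, because no scheduled test would show it before the course ends. Symptomatic anemia can still be caught clinically.

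The size is small: about 1.4 mild cases in 75 over the course if the 1.9% rate carries over (0.75 to 2.25 over an assumed 1% to 3%), and an unknown number by week 4, from 0 to 1.4 at 1.9%. The documents cannot show that even one participant would be at the wrong dose, and the expected harm is slight. This is a low-cost safety improvement and does not threaten the trial's conclusions.

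**What to change.** Add a complete blood count, or at least hemoglobin, to the week-4 and week-8 draws already taken for ALT and drug level. Have the investigator review and classify the week-4 result for clinical significance, as Section E.5 already requires for laboratory reports, before the dose goes up. Apply the existing tolerability condition and reduce-or-stop rule to a clinically significant new decline. Any threshold for holding the dose must be written down by the sponsor, for example the local laboratory's lower limit, because the screening exclusion in Section E.1.a has no cut-off to borrow.

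The cost is about 75 × 2 = 150 extra counts, with no added visit or needle stick. The drawback is that perhaps one or two participants would be held at 4 mg, against the aim of studying the maximum dose. Report that non-random dose difference and check it in a sensitivity analysis of response, for example with and without participants who did not reach 8 mg. Do not treat drug-level adjustment as having dealt with it.

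If the sponsor prefers not to add the counts, Section E.1.c should say that interim monitoring for anemia is by symptoms only. That removes the ambiguity but leaves symptom-free cases undetected until week 12.
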